4.1.2 Secondary Endpoints

- (1) Clinical remission at week 8 and 56
- (2) Steroid-free remission at week 8 and 56
- (3) Steroid-free response at week 8 and 56
- (4) Mucosal healing at week 8 and 56
- (5) The change of partial Mayo score from baseline to week 56
- (6) The change of full Mayo score from baseline to week 56
- (7) The change of fecal calprotectin, hemoglobin, albumin, CRP, and ESR level from baseline to week 56
- (8) The change of the composition of Fecal micro biota from baseline to week 56

4.2 Safety

Adverse events

5. Assessment Methods

5.1 Effectiveness Assessment

The subjects participating in this study will be followed up at weeks 8, 16, 24, 32, 40, 48, and 56 according to the clinical procedure after enrollment. (The window period of each follow-up is ± 1 week.) At baseline, demographic, disease, and drug-related data will be collected. Additionally, the Mayo score will be measured along with the routine laboratory tests.

For the enrolled subjects, 160 mg will be administered at the time of enrollment, 80 mg 2 weeks after the first dose, and 40 mg biweekly thereafter, according to the Korean authorization details. At week 8, the clinical

| dreamcis ATIGERMED COMPANY | | Last Update Date |
|----------------------------------|--|------------------|
| | CONFIDENTIAL: | |
| | THIS DOCUMENT AND THE INFORMATION CONTAINED HEREIN ARE | 02-NOV-2018 |
| | PROPRIETARY TO THE COMPANY AND ARE NOT TO BE DISCLOSED | 02-INO V-2018 |
| | WITHOUT THE WRITTEN PERMISSION OF THE COMPANY. | |
| STATISTICAL ANALYSIS PLAN (V2.0) | | |

response will be assessed. At this time, the subjects with a clinical response will be able to continue adalimumab treatment according to the Korean insurance coverage standards, and will be followed up through this study.

The clinical response is defined as 3 points or more reduction and 30% or more reduction in the full Mayo score (endoscopic findings, stool frequency, rectal bleeding, physician's global assessment) at week 8 from the baseline plus 1 point or more reduction in the rectal bleeding subscore or an absolute rectal bleeding subscore of 1 point or less.

At every follow-up visit, the partial Mayo score (stool frequency, rectal bleeding, physician's global assessment) will be measured to observe the effect of adalimumab, and routine laboratory tests will be conducted according to the routine treatment procedures.

At baseline, week 8, week 56, and when there is an inadequate response, the full Mayo score will be measured with endoscopy, which will also be conducted according to the routine treatment procedures.

5.2 Safety Assessment

An adverse event (AE) is defined as an unusual medical event that occurred in a subject, and is not necessarily causally related to the drug. Therefore, AEs are undesirable and unintended signs (including abnormal clinical test values), symptoms, or temporary illnesses, regardless of the causality with the use of the drug.

Such AEs may not only be due to unintentional or intentional overdose, drug abuse, and discontinuation of the drug but may also be caused by the use of a drug in accordance with the authorization details within the product instruction. Deterioration of the existing disease and conditions is also considered an AE.

6. Statistical Analysis Methods

All statistical analyses will be performed with the SAS software version 9.4 or higher. For all the statistical tests, two-sided tests will be conducted at the 0.05 significance level. Where applicable, an analytical method will be employed depending on whether or not to satisfy the normality assumptions.

For the continuous variables, the number of subjects, mean, standard deviation, median, 1st quartile, 3rd quartile, minimum, and maximum values will be presented. For the categorical variables, the frequency and percentage will be presented. The figures with decimal places, such as the mean, standard deviation, and percentage, will be rounded off to the second decimal place, and the p-value will be rounded off to the fourth decimal place.

| dreamcis ATIGERMED COMPANY | | Last Update Date |
|----------------------------------|---|------------------|
| | CONFIDENTIAL: THIS DOCUMENT AND THE INFORMATION CONTAINED HEREIN ARE PROPRIETARY TO THE COMPANY AND ARE NOT TO BE DISCLOSED. | 02-NOV-2018 |
| | WITHOUT THE WRITTEN PERMISSION OF THE COMPANY. | 02 110 7 2010 |
| STATISTICAL ANALYSIS PLAN (V2.0) | | |

When day is converted to month, it will be based on 30 days per month.

6.1 Distribution of Study Subjects

The frequencies and percentages of the number of subjects enrolled, the ITT set and the reason for exclusion therefrom, and the PP set and the reason for exclusion therefrom will be presented.

6.2 Demographic Characteristics

Descriptive statistics will be obtained for the demographic data and health status in the ITT set. For the continuous data, the mean, standard deviation, median, 1st quartile, 3rd quartile, minimum, and maximum values will be obtained, while for the categorical data, the frequencies and percentages will be calculated.

The variables representing demographic data are as follows:

- (1) Continuous Data
- <Basic and Disease Information>
 - Age (years)
 - Onset age (years)^a
 - Height (cm)
 - Weight (kg)
 - BMI (kg/m²)
 - Disease duration (months)^b
 - Full Mayo score (endoscopic findings, stool frequency, rectal bleeding, physician's global assessment) at baseline
 - Initial fecal calprotectin level
 - Laboratory tests (hemoglobin (g/dl), albumin (g/dl), ESR (mm/hr), CRP (mg/dl))
 - Adalimumab trough level (μg/mL)^c
 - Antibody adalimumab (μg/mL)^d

<Medication Administration Information>

- Total administration period (days)^e
- Total administration frequency (times)
- Total administration dose (mg)
- Period to dose escalation (days)^f

| -4 | | Last Update Date |
|-------------------|--|------------------|
| | CONFIDENTIAL: | |
| dreamcis | THIS DOCUMENT AND THE INFORMATION CONTAINED HEREIN ARE | 00 31031 0010 |
| ATIGERMED COMPANY | PROPRIETARY TO THE COMPANY AND ARE NOT TO BE DISCLOSED | 02-NOV-2018 |
| | WITHOUT THE WRITTEN PERMISSION OF THE COMPANY. | |
| CTATICTICA | I ANALVOIC DI AN (V/) () | |

STATISTICAL ANALYSIS PLAN (V2.0)

(2) Categorical Data

<Basic and Disease Information>

- Gender (male/female)
- Age (19-29 years / 30-39 years / 40-49 years / 50-59 years / \geq 60 years)
- Family history of UC (yes / no / unknown)
- UC extent (proctitis / left-sided colitis / extensive colitis / others)
- Co-morbidities (yes/no/unknown) and details⁹
- Study completion (yes/no) and reason for study discontinuation (loss of follow-up/inadequate response/ withdrawal of patient consent/others)

<Medication Administration Information>

- Previous medication for UC (yes/no/unknown) and details

 (Systemic steroids/antibiotics/non-biologics (5-ASA/methotrexate/azathioprine/6-mercaptopurine/cyclosporine/tacrolimus) / biologics^h (1 medication / 2 medication and above) / others)
- Concomitant medication for UC (yes/no) and details^g
 (5-ASA / methotrexate / azathioprine / 6-mercaptopurine / cyclosporine / tacrolimus / steroid (20 mg and above (daily dose) / less than 20 mg (daily dose))
- Administration status
 (First dose (80/160 mg), second dose (40mg/80mg), dose escalation (yes/no), administration frequency
 (2 times and below / more than 2 times), reason for discontinuation (inadequate response / adverse event / others))
- TNF antagonist naivety (yes/no)
- * The categories can be modified according to the structure and characteristics of the collected data.

^a Onset age: The period from the date of birth to the date of diagnosis

^b Disease duration: The period from the date of diagnosis to the date of consent of the subject

 $^{^{}c}$ Adalimumab trough level: The below the quantification limit (BQL) value of the adalimumab trough level is <0.040 μ g/mL. If collected like this, it is analyzed by replacing it with 0.040 μ g/mL, and the total number of replacements will be specified.

d Antibody adalimumab: The below the quantification limit (BQL) value of antibody adalimumab will be confirmed at the central lab after the final data collection is completed. The data at the BQL will be analyzed by replacing them with the lowest measurable value, and the total number of replacements will be specified.

^e Total administration period: It is calculated as the period from the administration start date to the administration end date, and if administration is ongoing, the administration end date is replaced with the last visit date.

^f Period to dose escalation: The period from the administration start date to the first dose escalation (every 1 week)

| dreamcis ATIGERMED COMPANY | | Last Update Date |
|-------------------------------|--|------------------|
| | CONFIDENTIAL: THIS DOCUMENT AND THE INFORMATION CONTAINED HEREIN ARE | |
| | PROPRIETARY TO THE COMPANY AND ARE NOT TO BE DISCLOSED | 02-NOV-2018 |
| | WITHOUT THE WRITTEN PERMISSION OF THE COMPANY. | |
| STATISTICA | LANALYSIS PLAN (V2 0) | |

^g The classification of the co-morbidities and concomitant medications for UC is presented with the terms classified based on the dictionary specified in the latest version of DMP. Here, the co-morbidities and concomitant medications are summarized with the system organ class (SOC) and preferred term (PT) based on the MedDRA classification. The concomitant medications for UC are summarized with anatomical

h Biologics: Single-dose infliximab or a single dose of another medication is classified as 1 medication, and if infliximab and another medication are both administered, it is classified as 2 medications and above.

therapeutic chemical 1 (ATC1) and anatomical therapeutic chemical 2 (ATC2) based on the WHODDE classification.

6.3 Effectiveness Endpoint Analysis Method

6.3.1 Primary Effectiveness Endpoint

- (1) The frequency and percentage of the subjects who showed a clinical response^a at visit 2 (week 8) will be presented, and the 95% confidence interval will be calculated.
- (2) The frequency and percentage of the subjects who showed a persistent clinical response^a at visit 2 (week 8), visit 4 (week 24), and visit 8 (week 56) will be presented, and the 95% confidence interval will be calculated.

Here, if any item in either the full or partial Mayo score was not collected, the subject will be excluded from this analysis.

^a Clinical response: It is defined as the case with 3 points or more reduction and 30% or more reduction in the full Mayo score at visit 2 (week 8) from visit 1 (baseline) plus 1 point or more reduction in the rectal bleeding subscore or an absolute rectal bleeding subscore of 1 point or less.

^b Persistent clinical response: Defined as the case of 3 points or more reduction and 30% or more reduction in the full Mayo score both at visit 2 (week 8) and visit 8 (week 56) from visit 1 (baseline) plus 1 point or more reduction in the rectal bleeding subscore or absolute rectal bleeding subscore of 1 point or less. At visit 4 (week 24), however, it is defined as the case of 2 points or more reduction and 30% or more reduction in the partial Mayo score plus 1 point or more reduction in the rectal bleeding subscore or an absolute rectal bleeding subscore of 1 point or less.

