### **9.2.2 Drop-Out Subjects**

Once a subject is dropped out from the study, no further information for that subject will be collected. However, the reason for drop-out will be reported and serious adverse events will be reported to AbbVie until 70 days following the intake of the last dose of adalimumab.

Subjects will be dropped out from the study:

- 1) If the subjects choose to withdraw from the study
- 2) Where ethical or practical conflicts hinder the procedure of the study, and such cases will be determined based on the investigator's judgment
- 3) In case of Adalimumab discontinuation at any point during study period

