6.3.2 Secondary Effectiveness Endpoint

If any item in either the full or partial Mayo score was not collected, the subject will be excluded from the relevant secondary effectiveness endpoint analysis.

(1) Percentage (%) of subjects who showed clinical remission^c at visit 2 (week 8) and who showed clinical remission^c at visit 4 (week 24) and visit 8 (week 56) among those who showed a clinical response at visit 2 (week 8)

CONFIDENTIAL:

THIS DOCUMENT AND THE INFORMATION CONTAINED HEREIN ARE PROPRIETARY TO THE COMPANY AND ARE NOT TO BE DISCLOSED WITHOUT THE WRITTEN PERMISSION OF THE COMPANY.

02-NOV-2018

Last Update Date

STATISTICAL ANALYSIS PLAN (V2.0)

The frequency and percentage of subjects who showed clinical remission^c at visit 2 (week 8) will be presented. Among the subjects who showed a clinical response at visit 2 (week 8), the frequency and percentage of those who showed clinical remission^c at visit 4 (week 24) and visit 8 (week 56) will also be presented.

^c Clinical remission: Defined as the case of full Mayo score ≤2 points and each subscore ≤1 point. For visit 4 (week 24), however, it is defined as the case of partial Mayo score ≤2 points and each subscore ≤1 point.

(2) Percentage (%) of subjects who showed a clinical response at visit 2 (week 8) without steroid administration^d, and who showed a clinical response at visit 4 (week 24) and visit 8 (week 56) without steroid administration^d among those who showed a clinical response at visit 2 (week 8)

The frequency and percentage of subjects who showed a clinical response at visit 2 (week 8) without steroid administration^d will be presented. Among these subjects, the frequency and percentage of those who showed a clinical response at visit 4 (week 24) and visit 8 (week 56) without steroid administration^d will also be presented.

^d Clinical response without steroid administration: Defined as the case where the subject showed a clinical response without using systemic steroids within 12 weeks before he/she was evaluated. For visit 2 (week 8), however, it is defined as the case where the subject showed a clinical response without using systemic steroids within 8 weeks before he/she was evaluated.

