The frequency and percentage of subjects who showed a clinical response at visit 2 (week 8) will be presented by classifying the subjects into two groups depending on the TNF antagonist naivety, and the 95% confidence interval for the result will be calculated. Additionally, the frequency and percentage of subjects who showed a persistent clinical response at visit 2 (week 8), visit 4 (week 24), and visit 8 (week 56) will be presented for each group, and the 95% confidence interval for the result will be calculated. Chi-square test or Fisher's exact test will be performed to determine if there is a difference in the clinical response rate between the two groups.

(5) Clinical remission at each visit depending on the TNF antagonist naivety

The frequency and percentage of subjects who showed clinical remission at visit 2 (week 8) will be presented by classifying the subjects into two groups depending on the TNF antagonist naivety. Among the subjects who showed a clinical response at visit 2 (week 8), the frequency and percentage of those who showed clinical remission at visit 4 (week 24) and visit 8 (week 56) will also be presented for each group. Chi-square test or Fisher's exact test will be performed to check if there is a difference in the clinical remission rate between the two groups.

(6) Clinical response without steroid administration at each visit depending on the TNF antagonist naivety

The frequency and percentage of subjects who showed a clinical response without steroid administration at visit 2 (week 8) will be presented by classifying the subjects into two groups depending on the TNF antagonist naivety. Among the subjects who showed a clinical response at visit 2 (week 8), the frequency and percentage of those who showed a clinical response without steroid administration at visit 4 (week 24) and visit 8 (week 56) will also be presented for each group. Chi-square test or Fisher's exact test will be performed to determine if there is a difference in the clinical response rate without steroid

| | | Last Update Date |
|----------------------------------|---|------------------|
| dreamcis ATIGERMED COMPANY | CONFIDENTIAL: THIS DOCUMENT AND THE INFORMATION CONTAINED HEREIN ARE PROPRIETARY TO THE COMPANY AND ARE NOT TO BE DISCLOSED. | 02-NOV-2018 |
| | WITHOUT THE WRITTEN PERMISSION OF THE COMPANY. | 02 1.0 . 2010 |
| STATISTICAL ANALYSIS PLAN (V2.0) | | |

administration between the two groups.

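### The exclusion rule in SAP 6.3.1 and 6.3.2 makes the week-56 ITT rates observed-case rates, and it conflicts with the plan's other missing-data rules

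*SAP*

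**What the plan says.** **Who is in the analysis.** Under SAP 2.5.1 (and protocol 9.7), the ITT set is all subjects dosed at least once for week 8, and all week-8 responders for week 56. The week-56 PP set (SAP 2.5.2) is those who completed evaluation and follow-up without a major deviation.

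**Who is taken out.** SAP 6.3.1, primary endpoint: "Here, if any item in either the full or partial Mayo score was not collected, the subject will be excluded from this analysis." SAP 6.3.2, for an uncollected Mayo item: "the subject will be excluded from the relevant secondary effectiveness endpoint analysis." SAP 6.3.1(2) states no denominator of its own.

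**What happens on stopping.** Protocol 9.2.2 lists as a reason for drop-out: "In case of Adalimumab discontinuation at any point during study period" (repeated in SAP 3). It also states: "Once a subject is dropped out from the study, no further information for that subject will be collected." Only the reason for drop-out and serious adverse events are still reported.

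**What is done with missing values.**
- SAP 6.6 carries the last value forward (LOCF) for missing partial-Mayo items, without limiting this to subjects on treatment. A missing endoscopic subscore is left missing.
- Protocol 9.7, General Considerations, leaves missing values missing. The protocol abstract says the same.
- Protocol 9.7, under the baseline heading, says non-responder imputation (NRI) and LOCF will be used. The SAP never mentions NRI.

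**Week 24.** SAP 6.3.1, footnote b, defines response at this visit from the partial score alone: "2 points or more reduction and 30% or more reduction in the partial Mayo score," plus the rectal-bleeding condition.

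**Steroid-free response at weeks 24 and 56.** The heading of SAP 6.3.2(2) takes the percentage "among those who showed a clinical response at visit 2 (week 8)." The text below it, after describing steroid-free week-8 responders, continues: "Among these subjects, the frequency and percentage of those who showed a clinical response at visit 4 (week 24)." SAP 6.5(6) says for the same endpoint: "Among the subjects who showed a clinical response at visit 2 (week 8), the frequency and percentage of those who showed a clinical response."

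**The concern.** A week-8 responder who stops adalimumab belongs to the week-56 ITT set by definition and is removed from the week-56 percentage by rule. Inadequate response is a listed reason for stopping (SAP 6.2), and under protocol 9.3 subjects unresponsive to dose escalation may stop on the physician's judgement. Some of those removed are therefore likely to be failures, and upward bias against the true rate is to be expected. It is not certain, because others will be missing through withdrawal of consent or because no endoscopy was done in routine practice.

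At stake are the second primary endpoint and the week-56 remission and healing rates. Each headline percentage would carry an ITT label on a completer base, as would the 95% confidence interval for response. Comparing ITT with PP would not show the effect, since both are close to completers. Because the documents contain several incompatible rules, two analysts could also report different week-24 and week-56 rates from the same data.

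**Working it through.** **Inputs from the documents.** N = 147, response 75%, 95% confidence interval of full width 15 points, drop-out 5% (protocol 9.5, SAP 2.4).

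**The plan's own figure.** The exact (Clopper-Pearson) interval at 75% first has a full width of at most 0.15 at n = 139 (width 0.14999). 139 / 0.95 = 146.3, rounded up to 147. The stated size is reproduced.

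**Base.** 147 × 0.95 = 139.65, taken as 139. 0.75 × 139 = 104.25, taken as 104 week-8 responders (R).

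**Assumptions.** The documents give neither the share of responders missing at week 56 nor the response among those assessed. I take 5% to 30% missing and 80% response, with 70% to 90% as a range.

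**Formula.** With m missing, n = R − m assessed and x responders among them, the observed-case rate is x/n and the rate over all responders is x/R. Since n ≤ R, the first is never below the second. The gap equals (x/n) × (m/R).

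**Week 56, R = 104:**

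| Missing | Observed-case (Wald half-width) | Over all 104 | Gap, points | Gap at 70–90% response |
|---|---|---|---|---|
| 5 (5%) | 79/99 = 79.8% (7.9) | 76.0% | 3.8 | 3.4–4.3 |
| 10 (10%) | 75/94 = 79.8% (8.1) | 72.1% | 7.7 | 6.8–8.7 |
| 21 (20%) | 66/83 = 79.5% (8.7) | 63.5% | 16.1 | 14.1–18.2 |
| 31 (30%) | 58/73 = 79.5% (9.3) | 55.8% | 23.7 | 20.8–26.9 |

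Without the initial 5% discount, R = 0.75 × 147 = 110, and the gaps at 80% response are 4.4, 8.0, 15.9 and 24.2 points.

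**Week 8.** The same rule removes dosed subjects without a complete week-8 score. At the plan's own 75% and 5%, the gap is 0.75 × 5 = 3.75 points.

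**Week 24, same subjects under three rules.** Under LOCF the result depends on how many carried-forward week-8 or week-16 scores meet the response definition: the lower limit is none, x/104, and the upper limit is all, (x + m)/104.

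| Missing | Exclusion (SAP 6.3.1) | NRI (protocol 9.7) | LOCF (SAP 6.6) |
|---|---|---|---|
| 5 | 79.8% | 76.0% | 76.0–80.8% |
| 10 | 79.8% | 72.1% | 72.1–81.7% |
| 21 | 79.5% | 63.5% | 63.5–83.7% |

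**Subjects on treatment without endoscopy.** Counting every missing subject as a failure can also mislead. Take 21 of 104 missing and x = 66, with k of the 21 on treatment and the rest discontinued and failed. If the k respond at 80%, the true rate is (66 + 0.8k)/104. Error in points against that rate:

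| k | True rate | SAP exclusion, 66/83 | All as non-responders, 66/104 | Exclude only the k, 66/(104 − k) |
|---|---|---|---|---|
| 5 | 67.3% | +12.2 | −3.8 | −0.6 |
| 10 | 71.2% | +8.4 | −7.7 | −0.9 |
| 11 | 71.9% | +7.6 | −8.5 | −1.0 |
| 21 | 79.6% | −0.1 | −16.2 | −0.1 |

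If the k are all true failures, the true rate is 63.5%. Counting them as non-responders is then exact, and excluding them overstates by 3.2, 6.8, 7.5 and 16.1 points. The documents give no split, so neither treatment of this group is shown to be better.

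**Steroid-free response.** This needs no arithmetic: the heading of SAP 6.3.2(2) and SAP 6.5(6) divide by all week-8 responders, while the text of 6.3.2(2) divides by the steroid-free responders only.

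**The case against.** - **The NRI sentence is weak evidence of intent.** It sits under the baseline heading, where NRI has no meaning, and both protocol 9.7 General Considerations and the abstract leave missing values missing. This stands: the SAP's exclusion agrees with most of the protocol's statements. The protocol still contradicts itself, and the week-56 problem does not depend on the NRI sentence.
- **SAP 6.6 may be meant to apply first, with 6.3.1 removing whoever is still incomplete.** That reading is possible and would give one rule at week 24, though an unrestricted one that lets a discontinuer count as a responder. It does not help at week 56, because the endoscopic subscore stays missing.
- **Week 24 carries less weight.** SAP 4.1 makes that analysis conditional, and the protocol has no week-24 primary endpoint. True, but SAP 4.1.1 lists week 24 as primary.
- **A full Mayo score is planned at inadequate response** (protocol 9.3, SAP 5.1), so some failures may be documented. The SAP does not assign that score to week 56, so it does not fill the gap.
- **The large gaps are assumed.** Correct. At the only documented figure, 5%, the gap of 3.8 points is about half the 7.9-point half-width. In one scenario (all 21 missing subjects on treatment, responding at 80%) the SAP rule is almost exact.
- **This is a descriptive single-arm study and readers can recompute.** Largely true: frequencies are planned, and SAP 6.1 and 6.2 tabulate exclusions and reasons for stopping. The headline percentage and its interval would nevertheless stay on the reduced base under an ITT label.
- **Counting every drop-out as a failure is a convention.** It is, and it is too harsh on those who leave for unrelated reasons. That argues for showing both rates, not for keeping the present rule.

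**Conclusion.** The concern holds. By the plan's own rules, a week-8 responder who stops adalimumab is in the week-56 ITT set and out of the week-56 percentage. The ITT rates for response, remission and mucosal healing are observed-case rates, never lower than the rate that counts discontinuers as non-responders.

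The size depends on two quantities the documents do not give. At 80% response among those assessed, the gap is 3.8 points at the plan's 5% drop-out figure. At an assumed 10% it is 7.7 points, about the ±7.5 points for which the study was sized (15 / 2). At an assumed 20% it is 16.1 points, and the reported Wald interval of 79.5 ± 8.7 (70.8–88.2%) would exclude the 63.5% rate over all responders.

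The conflict between SAP 6.3 and 6.6 and the two denominators in SAP 6.3.2(2) are secondary but real, since each permits different results from the same data. Because a primary endpoint is affected, the rules should be settled before analysis.

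**What to change.** Replace the exclusion sentences in SAP 6.3.1 and 6.3.2. For binary endpoints in the ITT set:

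1. Use as denominators all treated subjects at week 8 and all week-8 responders at weeks 24 and 56.
2. Count subjects who discontinued adalimumab or dropped out before the assessment as non-responders.
3. In SAP 6.6, limit LOCF to isolated missing partial-Mayo items in subjects still on treatment.
4. For subjects on treatment whose score still cannot be computed (for example, no endoscopy), report the number by reason and show the rate both with them as non-responders and with them excluded. The sponsor chooses the main analysis before the data are analysed.
5. Keep the observed-case rate as a labelled sensitivity analysis.

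Reconcile SAP 6.3.1, 6.3.2 and 6.6 with the two missing-data statements in protocol 9.7. Give SAP 6.3.2(2) one denominator, consistent with SAP 6.5(6).

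**Cost.** SAP wording, a short clarification of protocol 9.7 and extra table columns. No new data are needed, since reasons for drop-out and discontinuation are already collected. The downside is a lower headline rate, which will be too low to the extent that subjects dropped out for reasons unrelated to response.
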